### **9.3.3.1 Neurodevelopmental disorders, including autism spectrum disorder - additional considerations**

**Offspring exposure/intake to AEDs and diagnosis of epilepsy.** The neurodevelopmental effects of postnatal exposure to AEDs are not completely understood (30). However, AEDs may independently be associated with neuropsychiatric adverse effects (31). Therefore, the main analysis will be restricted to children unexposed to AEDs after birth and with no diagnosis of epilepsy.

Since the potential for reverse causality may apply and since there is likely to be correlation between epilepsy and NDD, exclusion of children receiving AED therapy or with a diagnosis of epilepsy could result in the introduction of selection bias. It is not anticipated that the proportion of children diagnosed with epilepsy and/or receiving AED exposure across the valproate and comparator groups will be differential so the likely impact on the hazard ratio (HR) will be minimal. However, a sensitivity analysis (see section 9.7.5) will be performed to explore the potential impact of having excluded children exposed to AEDs and/or diagnosed with epilepsy as there remains potential suspicion of possibly higher rates of NDD (31), compared to those children without such exposure to the treatment.

### **9.3.3.2 Congenital malformations - additional considerations**

**Maternal exposure to teratogenic activity/foetal toxicity.** Offspring maternally exposed (three months prior to conception or during pregnancy) to drugs with known teratogenic (32) activity/foetal toxicity (see Annex 3. Additional Information) are at risk of developing the outcomes of interest for reasons other than valproate, i.e. due to intake of other drugs associated with the CM. These offspring will be excluded from the comparative, sensitivity and exploratory objective analyses.

**Paternal exposure to teratogenic activity.** Paternal exposure to prescription medications, has not been associated with birth defects (3). Nevertheless, offspring from fathers exposed (three months prior to conception) to drugs with known teratogenic (32) activity (based on literature regarding maternal exposure) (see Annex 3. Additional Information) will be excluded from the comparative, sensitivity and exploratory objective analyses.

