### Exploratory objectives

[figure not shown]
5. To describe the putative risk factors and frequency of NDD, including ASD, as well as CM in offspring paternally exposed to valproate (in combination with other AEDs) and to other AEDs (in combination with other AEDs, excluding valproate) at the time of conception.
6. To describe the risk factors and frequency of NDD, including ASD, as well as CM in paternally and maternally matched exposure-discordant (valproate vs lamotrigine/levetiracetam monotherapy) siblings at conception.
7. Investigate the risk of CM in live offspring paternally exposed to valproate (monotherapy), compared to lamotrigine or levetiracetam (composite monotherapy) treatment at the time of conception in Sweden.
8. To describe the frequency of CM by target body system organ class in live and non-live offspring paternally exposed to valproate (monotherapy), and to lamotrigine or levetiracetam (composite monotherapy) treatment at the time of conception.

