#### **9.7.4 Exploratory objective analyses**

For the *exploratory analyses*, offspring maternally exposed to AEDs (including valproate, lamotrigine and levetiracetam) *in utero*, or during 3 months prior conception, as well as offspring from a mother with a history of epilepsy, will be excluded. For the *exploratory analyses related to the primary outcome*, offspring exposed to AEDs and/or diagnosed with epilepsy after birth will be excluded.

For exploratory objective 5, for offspring paternally exposed to AED polytherapy, summary cohort characteristics and univariate analysis (section 9.7.3.1) will be performed to describe the putative risk factors and frequency of the primary composite outcome (NDD, including ASD) and for the secondary composite outcome (CM) for offspring paternally exposed to valproate (in combination with other AEDs excluding lamotrigine and levetiracetam) and offspring paternally exposed to levetiracetam/lamotrigine in polytherapy (i.e. polytherapy including at least one of them, and excluding valproate) at the time of conception.

For exploratory objective 6, to explore potential for unmeasured family-related confounding factors (such as genetic liability for neuropsychiatric conditions or congenital malformations and early postnatal environmental influences), an exploratory sibling-matched descriptive analyses will be conducted, separately, on the primary composite outcome (NDD, including ASD) and the secondary composite outcome (CM) whereby only families with paternal valproate exposure-discordant siblings will be included (at least one offspring with paternal valproate exposure and one offspring without exposure). For this analysis, summary cohort characteristics and univariate analysis (section 9.7.3.1) will be performed to describe the subgroups and identify potential risk factors for the composite primary and secondary outcomes of interest, respectively.

For exploratory objective 7, which is to investigate the risk of CM in live offspring paternally exposed to valproate (monotherapy), compared to lamotrigine or levetiracetam (composite monotherapy) treatment at the time of conception in Sweden, the descriptive (section 9.7.2), and comparative (section 9.7.3.2) analyses will be presented separately. This is because the population for analysis is comprised of live births only and therefore is systematically different to the cohorts for CM analysis in Norway and Denmark

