**Table 56: Teratogens**

ATC code	Name (5 th level ATC, chemical substance)	2 nd level ATC, therapeutic subgroup	1 st level ATC, anatomical main group
A01AB04	amphotericin	Stomatological preparations	Alimentary tract and metabolism
A01AB08	neomycin	Stomatological preparations	Alimentary tract and metabolism
A01AB13	tetracycline	Stomatological preparations	Alimentary tract and metabolism
A01AB21	chlortetracycline	Stomatological preparations	Alimentary tract and metabolism
A01AB22	doxycycline	Stomatological preparations	Alimentary tract and metabolism

ATC code	Name (5th level ATC, chemical substance)	2nd level ATC, therapeutic subgroup	1st level ATC, anatomical main group
A01AB23	minocycline	Stomatological preparations	Alimentary tract and metabolism
A01AD05	aspirin = acetylsalicylic acid	Stomatological preparations	Alimentary tract and metabolism
A02BA04	nizatidine	Drugs for acid related disorders	Alimentary tract and metabolism
A02BB01	misoprostol	Drugs for acid related disorders	Alimentary tract and metabolism
A02BC01	omeprazole	Drugs for acid related disorders	Alimentary tract and metabolism
A02BC02	pantoprazole	Drugs for acid related disorders	Alimentary tract and metabolism
A02BC03	lansoprazole	Drugs for acid related disorders	Alimentary tract and metabolism
A02BC05	esomeprazole	Drugs for acid related disorders	Alimentary tract and metabolism
A03AD01	papaverine	Drugs for functional gastrointestinal disorders	Alimentary tract and metabolism
A04AA03	tropisetron	Antiemetics and anti-nauseants	Alimentary tract and metabolism
A04AA55	netupitant and palonosetron = palonosetron, combinations	Antiemetics and anti-nauseants	Alimentary tract and metabolism
A05AA01	chenodeoxycholic acid	Bile and liver therapy	Alimentary tract and metabolism
A05AA02	ursodeoxycholic acid	Bile and liver therapy	Alimentary tract and metabolism
A06AX06	tegaserod	Drugs for constipation	Alimentary tract and metabolism
A07AA01	neomycin	Intestinal anti-infectives	Alimentary tract and metabolism
A07AA04	streptomycin	Intestinal anti-infectives	Alimentary tract and metabolism
A07AA07	amphotericin	Intestinal anti-infectives	Alimentary tract and metabolism
A07AA08	kanamycin	Intestinal anti-infectives	Alimentary tract and metabolism

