N03AD01	ethosuximide	Antiepileptics	Nervous system
N03AD02	phensuximide	Antiepileptics	Nervous system
N03AD03	methsuximide = mesuximide	Antiepileptics	Nervous system
N03AE01	clonazepam	Antiepileptics	Nervous system
N03AF01	carbamazepine	Antiepileptics	Nervous system
N03AF02	oxcarbazepine	Antiepileptics	Nervous system
N03AF03	rufinamide	Antiepileptics	Nervous system
N03AG04	vigabatrin	Antiepileptics	Nervous system
N03AG06	tiagabine	Antiepileptics	Nervous system
N03AX03	sultiame	Antiepileptics	Nervous system
N03AX11	topiramate	Antiepileptics	Nervous system
N03AX12	gabapentin	Antiepileptics	Nervous system
N03AX15	zonisamide	Antiepileptics	Nervous system
N03AX16	pregabalin	Antiepileptics	Nervous system
N03AX17	stiripentol	Antiepileptics	Nervous system
N03AX18	lacosamide	Antiepileptics	Nervous system
N03AX21	ezogabine = retigabine	Antiepileptics	Nervous system
N03AX22	perampanel hemisquihydrate = perampanel	Antiepileptics	Nervous system
N03AX23	brivaracetam	Antiepileptics	Nervous system
N04BA01	levodopa	Anti-parkinson drugs	Nervous system

ATC code	Name (5 th level ATC, chemical substance)	2 nd level ATC, therapeutic subgroup	1 st level ATC, anatomical main group
N04BA02	benserazide and levodopa = levodopa and decarboxylase inhibitor	Anti-parkinson drugs	Nervous system
N04BA03	carbidopa, entacapone and levodopa	Anti-parkinson drugs	Nervous system
N04BB01	amantadine	Anti-parkinson drugs	Nervous system
N04BC02	pergolide	Anti-parkinson drugs	Nervous system
N04BC04	ropinirole	Anti-parkinson drugs	Nervous system
N04BC05	pramipexole	Anti-parkinson drugs	Nervous system
N04BC07	apomorphine	Anti-parkinson drugs	Nervous system
N04BC09	rotigotine	Anti-parkinson drugs	Nervous system
N04BD02	rasagiline	Anti-parkinson drugs	Nervous system
N04BD03	safinamide mesilate = safinamide	Anti-parkinson drugs	Nervous system
N04BX01	tolcapone	Anti-parkinson drugs	Nervous system
N04BX02	entacapone	Anti-parkinson drugs	Nervous system
N05AA01	chlorpromazine	Psycholeptics	Nervous system
N05AA03	promazine	Psycholeptics	Nervous system
N05AB02	fluphenazine	Psycholeptics	Nervous system
N05AB03	perphenazine	Psycholeptics	Nervous system
N05AB04	prochlorperazine	Psycholeptics	Nervous system
N05AB05	thiopropazate	Psycholeptics	Nervous system
N05AB06	trifluoperazine	Psycholeptics	Nervous system
N05AC01	periciazine	Psycholeptics	Nervous system
N05AC02	thioridazine	Psycholeptics	Nervous system
N05AD01	haloperidol	Psycholeptics	Nervous system

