**Table 57: AEDs excluding the study drugs**

ATC code	Name (5 th level ATC, chemical substance)	4 th level ATC, chemical subgroup
N03AA01	Methylphenobarbital	Barbiturates and derivatives
N03AA02	Phenobarbital	Barbiturates and derivatives

ATC code	Name (5th level ATC, chemical substance)	4th level ATC, chemical subgroup
N03AA03	Primidone	Barbiturates and derivatives
N03AA04	Barbexaclone	Barbiturates and derivatives
N03AA30	Metharbital	Barbiturates and derivatives
N03AB01	Ethotoin	Hydantoin derivatives
N03AB02	Phenytoin	Hydantoin derivatives
N03AB03	Amino(diphenylhydantoin) valeric acid	Hydantoin derivatives
N03AB04	Mephenytoin	Hydantoin derivatives
N03AB05	Fosphenytoin	Hydantoin derivatives
N03AB52	Phenytoin, combinations	Hydantoin derivatives
N03AB54	Mephenytoin, combinations	Hydantoin derivatives
N03AC01	Paramethadione	Oxazolidine derivatives
N03AC02	Trimethadione	Oxazolidine derivatives
N03AC03	Ethadione	Oxazolidine derivatives
N03AD01	Ethosuximide	Succinimide derivatives
N03AD02	Phensuximide	Succinimide derivatives
N03AD03	Mesuximide	Succinimide derivatives
N03AD51	Ethosuximide, combinations	Succinimide derivatives
N03AE01	Clonazepam	Benzodiazepine derivatives
N03AF01	Carbamazepine	Carboxamide derivatives
N03AF02	Oxcarbazepine	Carboxamide derivatives
N03AF03	Rufinamide	Carboxamide derivatives
N03AF04	Eslicarbazepine	Carboxamide derivatives
N03AG03	Aminobutyric acid	Fatty Acid derivatives
N03AG04	Vigabatrin	Fatty Acid derivatives
N03AG05	Progabide	Fatty Acid derivatives
N03AG06	Tiagabine	Fatty Acid derivatives
N03AX03	Sultiame	Other Antiepileptics
N03AX07	Phenacemide	Other Antiepileptics
N03AX10	Felbamate	Other Antiepileptics
N03AX11	Topiramate	Other Antiepileptics
N03AX12	Gabapentin	Other Antiepileptics
N03AX13	Pheneturide	Other Antiepileptics

ATC code	Name (5th level ATC, chemical substance)	4th level ATC, chemical subgroup
N03AX15	Zonisamide	Other Antiepileptics
N03AX16	Pregabalin	Other Antiepileptics
N03AX17	Stiripentol	Other Antiepileptics
N03AX18	Lacosamide	Other Antiepileptics
N03AX19	Carisbamate	Other Antiepileptics
N03AX21	Retigabine	Other Antiepileptics
N03AX22	Perampanel	Other Antiepileptics
N03AX23	Brivaracetam	Other Antiepileptics
N03AX24	Cannabidiol	Other Antiepileptics
N03AX30	Beclamide	Other Antiepileptics

ATC: Anatomical Therapeutic Chemical

Table 58: AEDs all

ATC code	Name (5th level ATC, chemical substance)	4th level ATC, chemical subgroup
N03AA01	methylphenobarbital	Barbiturates and derivatives

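### The paternal teratogen exclusion, as written, removes from the CM part of exploratory objective 5 every AED combination containing one of 26 of the 44 non-study AEDs, and depletes the two polytherapy groups unevenly

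*Protocol*

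**What the plan says.** Section 9.3.3.2 sets a paternal exclusion for the CM cohort. It covers offspring of fathers exposed in the three months before conception to drugs held to be teratogenic, and the sentence gives the basis of the list and the scope of the rule: "based on literature regarding maternal exposure) (see Annex 3. Additional Information) will be excluded from the comparative, sensitivity and exploratory objective analyses". The list is in Annex 3, under "Table 56: Teratogens". It includes AEDs, for example "carbamazepine"; valproate, lamotrigine and levetiracetam are not on it.

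Exploratory objective 5, in section 8, is to describe risk factors and frequency of NDD "as well as CM in offspring paternally exposed to valproate (in combination with other AEDs", alongside a group on other AED combinations without valproate. Section 9.7.4 narrows both groups. The first becomes "offspring paternally exposed to valproate (in combination with other AEDs excluding lamotrigine and levetiracetam". The second becomes polytherapy that contains lamotrigine or levetiracetam and does not contain valproate.

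Section 9.3.1 defines polytherapy as any AED combination, taken together or in sequence, within the three-month risk window. The possible partner drugs are in "Table 57: AEDs excluding the study drugs".

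**The concern.** The drug that places a father in a polytherapy group can be the same drug that excludes his offspring as teratogen-exposed. A father on valproate plus carbamazepine meets the group definition in section 9.7.4 and is then removed by section 9.3.3.2 because of the carbamazepine.

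The reason section 9.3.3.2 gives for the maternal rule is to remove CM risk that arises from drugs other than valproate. That logic suits a monotherapy comparison. In a description of polytherapy, the second AED is part of the exposure being described.

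The limitations text in section 9.9.2 answers the restriction to monotherapy by pointing to an exploratory description of AED polytherapy users. For CM, the exclusion works against that. Section 9.9.1 adds that Danish results based on fewer than five cases or observations will not be released, so smaller groups raise the risk that no Danish figure can be reported.

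**Working it through.** The protocol states no sample size or expected count for objective 5, so there is no figure to reproduce. The check is a comparison of code lists, followed by a comparison of the sections.

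**1. Do the windows coincide?** Polytherapy is defined over the three months before conception (section 9.3.1), and so is the paternal teratogen exposure (section 9.3.3.2). Footnotes 10, 14 and 15 use the same device for both: dispensations in the six months before conception count if they led to intake in the last three. A partner drug that is on Table 56 therefore always triggers the exclusion.

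**2. How many partner AEDs are on the teratogen list?** Table 57 has 44 codes. Those that also appear in Table 56, by subgroup:

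| Subgroup | On Table 56 | In Table 57 |
|---|---|---|
| N03AA barbiturates | 3 | 5 |
| N03AB hydantoins | 2 | 7 |
| N03AC oxazolidines | 2 | 3 |
| N03AD succinimides | 3 | 4 |
| N03AE benzodiazepine | 1 | 1 |
| N03AF carboxamides | 3 | 4 |
| N03AG fatty acid derivatives | 2 | 4 |
| N03AX other | 10 | 16 |
| Total | 26 | 44 |

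Listed share: 26/44 = 59%. Not listed: 44 − 26 = 18 (41%), namely N03AA04, AA30, AB01, AB03, AB05, AB52, AB54, AC03, AD51, AF04, AG03, AG05, AX07, AX10, AX13, AX19, AX24 and AX30. Eslicarbazepine, felbamate, fosphenytoin and cannabidiol are among them.

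**3. What happens to two-drug combinations?** These are counts of code pairs, not of patients.

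- Valproate group, section 9.7.4 definition: 44 possible partners, 26 removed, 18 left.
- Valproate group, section 8 wording, which does not bar lamotrigine or levetiracetam: 44 + 2 = 46 partners, 26 removed (26/46 = 57%), 20 left.
- Lamotrigine/levetiracetam group, section 9.7.4 definition: 2 × 44 + 1 = 89 pairs, 2 × 26 = 52 removed (58%), 2 × 18 + 1 = 37 left. The extra 1 is lamotrigine plus levetiracetam.

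Combinations of three or more drugs go as well if any one of them is listed.

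**4. Are the losses even?** The shares of code pairs are similar, but the survivors differ in kind. Lamotrigine plus levetiracetam stays in the second group. Under section 9.7.4 the valproate group keeps no pairing with another study drug.

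**5. Is the scope of the exclusion settled?** No.

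- Section 9.3.3.2 names the exploratory analyses.
- Section 9.3.3, in explaining why no polypharmacy score is calculated for CM, describes the parental teratogen exclusion as made for the comparative analyses.
- Section 9.7.4 lists its own exclusions for exploratory analyses and does not mention paternal teratogens.
- The note under Table 3 gives teratogenic drugs as an exclusion for the mother only.

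Two programmers working from sections 9.3.3.2 and 9.7.4 respectively would build different cohorts.

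**6. What would an exemption restore?** If N03A drugs were exempt for objective 5 (CM), 0 of the 44 partners would be removed on account of the partner AED.

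**The case against.** The strongest reply is that a larger conclusion would not follow. A reader might infer that the valproate polytherapy group is emptied, that the CM question in objective 5 cannot be answered, or that the other group shrinks to a single drug pair. The documents support none of these. Eighteen partner codes stay eligible in both groups, and the protocol gives no data on how often any partner AED is used. That the remaining codes are seldom used may be plausible, but it would be a judgement from outside the protocol. The second group keeps 37 code pairs, not one. Under the section 8 wording, valproate with lamotrigine or levetiracetam would also survive.

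It can also be said that the rule is ambiguous, since sections 9.3.3 and 9.7.4 imply a narrower scope. That is fair, but it does not remove the problem: section 9.3.3.2 is the section that defines the exclusion, and it names the exploratory analyses outright.

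Finally, objective 5 is exploratory and descriptive. No effect estimate or power claim depends on it, the exclusion applies to CM only, and the comparative analyses are restricted to monotherapy. This stands and limits the weight of the point.

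**Conclusion.** The conflict is real and sits in the current text. Taken as written, section 9.3.3.2 removes from the CM part of objective 5 every combination that includes one of 26 of the 44 non-study AEDs (59%). The valproate group additionally loses lamotrigine and levetiracetam as partners under section 9.7.4, while the pair lamotrigine plus levetiracetam remains in the other group. CM frequencies reported this way would describe a selected remainder and not AED polytherapy as the objective intends.

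The 59% is a share of drug codes. The share of offspring lost cannot be derived from the protocol. The conclusion assumes that section 9.3.3.2 governs; if the exclusion was in fact confined to the comparative analyses, the loss did not occur and only the contradictory wording remains. The NDD part of objective 5, the primary and secondary analyses and the other monotherapy comparisons are not affected. The point should be corrected, in proportion to a descriptive exploratory objective.

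**What to change.** - In sections 9.3.3.2 and 9.7.4, state that for exploratory objective 5 in the CM cohort the paternal teratogen exclusion does not apply to drugs in ATC group N03A. Keep the paternal exclusion for Table 56 drugs that are not AEDs, and keep the maternal exclusion as it is.
- Make sections 9.3.3, 9.3.3.2 and 9.7.4 and the note under Table 3 agree on which analyses the paternal exclusion covers.
- Make section 8 and section 9.7.4 agree on which partner drugs each polytherapy group may contain.
- Because Table 1 dates the final report and its second submission to January and March 2023, state which rule was applied in those outputs, and re-run the descriptive CM tables for objective 5 if the exclusion was applied to AEDs.

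Confining the paternal exclusion to the comparative analyses would also remove the conflict, but it would admit fathers exposed to non-AED teratogens as well.

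The cost is a few sentences, one filter change and a small re-run country by country. No new data are needed and no comparative analysis changes. The downside is that the groups will include AEDs listed as teratogenic on maternal evidence, which is inherent to describing AED polytherapy.

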### **9.3.3.3 Variables available in data source**

A summary description of the variables available for analysis is presented in Annex 3. Additional Information.

## **9.4 Data Sources**

The proposed sources of data are expected to provide a rich set of variables. Given the real-world, retrospective nature of the data, the availability of complete information is expected to vary.

All data elements for this study will be collected from information routinely recorded in the national registries of

---

 In order to account for potential dispensations that can have led to an intake during the 3 months look-back period under investigation, all dispensations that are recorded in the 6 months before conception that gave rise to a teratogenic drug intake during the 3 months prior to conception will be considered.

 See footnote 14

- Sweden
- Norway
- Denmark

Databases used in the study are listed in Table 5. Sweden will not be used in the secondary outcome cohort analysis due to lack of paternal linkage to non-live births.

**Table 5: Rationale and data source description by country**

Country	Data source	Type of data and brief description
Sweden	Multigenerational Register	Source of data for personal identifier for mothers, fathers and offspring, biologic vs adoptive parents, siblings, migration status and marital status. Source of linkage to father (available only for live births).
	Cause of Death Register	Source of data for vital status and further details on diagnosis or cause leading to spontaneous abortions or stillbirths.
	National Prescription registry	Source of data for all outpatient dispensations of prescription medications. Recorded information include data of dispensations, active substance using ATC code, amount sold, pack size and route of administration. Data available since 2005.
	National Patient Registry	Source of data for all diagnosis outcomes of interest in live births. The registry tracks discharge diagnoses with dates and information about procedures. The ICD-10 coding system has been used for the duration of our study period.
	Medical Birth Registry	Source of data for information on gestational age, birth weight, 5-minute Apgar score, live births, stillbirths, smoking during pregnancy, body mass index (BMI), date of conception (estimated from gestational age and date of birth), procedures connected to assisted fertilization.
Norway	Central Person Register	Source of data for personal identifier for mothers, fathers and children, vital status, migration status and marital status.
	Norwegian Prescription Database	Source of data for all outpatient dispensations of prescription medications. Recorded information include data of dispensations, active substance using ATC code, amount sold, pack size and route of administration. Data available since 2004.
	Norwegian Patient Registry	Source of data for all diagnosis outcomes of interest in live births. The registry tracks discharge diagnoses with dates and information about procedures. The ICD-10 coding system has been used for the duration of our study period. Data available for record linkage since 2008.
	Medical Birth Registry	Source of data for information on gestational age, birth weight, 5-minute Apgar score, live births, stillbirths, spontaneous abortions, smoking during pregnancy, body mass index (BMI), date of conception (estimated from gestational age and date of birth), assisted reproductive technology (ART). Source of linkage to father.
	Cause of Death Register	Source of data for vital status and further details on diagnosis or cause leading to spontaneous abortions or stillbirths.

Country	Data source	Type of data and brief description
Denmark	The Danish Civil Registration System	Source of data for personal identifier for mothers, fathers and children, vital status, migration status and marital status.
	Register of Medicinal Product Statistics (RMPS)	Source of data for all dispensations of prescription medications at community pharmacies at individual patient-level. Recorded information include data of dispensations, active substance using ATC code, amount sold, pack size and route of administration. Data available since 1995.
	National Patient Registry	Source of data for all diagnosis outcomes of interest at public and private hospitals (somatic and psychiatric wards). The registry tracks primary and secondary diagnoses with dates and information about procedures and treatment. The ICD-10 coding system has been used for the duration of our study period. Diagnoses at psychiatrists (and other specialists) who have their own private practice are not registered in the National Patient Registry.
	Cause of Death Register	Source of data for further details on diagnosis or cause leading to spontaneous abortions or stillbirths.
	Medical Birth Registry	Source of data for gestational age, birth weight, 5-minute Apgar score, live births, stillbirths, malformations, smoking during pregnancy, body mass index (BMI), date of conception (estimated from gestational age and date of birth). Source of linkage to father.
	The In Vitro Fertilisation Register	The IVF register contains information on IVF treatment carried out at public as well as private fertility clinics in Denmark. For IVF treatments resulting in pregnancy, information on birth, miscarriage or stillbirth is also available.

ATC: Anatomical Therapeutic Chemical; ICD-10: International Statistical Classification of Diseases and Related Health Problems 10th Revision; IVF: In Vitro Fertilisation

The data sources considered are routinely used for PASS requested by the EMA and the subject of many publications.

